1.0 Objectives

1.1 *Describe the purpose, specific aims, or objectives.*

We propose to study the effect of Acthar® on recovery from cognitive relapses in multiple sclerosis (MS). Cognitive relapses are acute clinical declines in concentration, memory, working memory or increased fatigue. Cognitive relapses may also be detected by the presence on brain MRI of new active supratentorial Gad enhancing lesions. We will use well-validated, objective metrics to evaluate cognitive changes following treatment with a 5-day course of Acthar® over three months in patients showing cognitive relapses in MS. To account for the possible practice effects of cognitive testing over a three-month period, we will compare the results to a matched sample of MS patients who are clinically stable.

1.2 *State the hypotheses to be tested.*

The primary hypothesis of the study is that due to enhanced melanocortin response, Acthar will facilitate recovery from cognitive changes occurring during cognitively focused relapse, and that patients treated with Acthar will return to baseline following treatment.

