11.0 Data Management

11.1 Describe the data analysis plan, including any statistical procedures.

Data will be processed by trained research assistants blind to study hypotheses. Analysis will be conducted using SPSS 22.0. Analysis strategy will be repeated measures analysis of variance where baseline, day 0 and day 90 scores are compared. Analysis of variance will be used

University at Buffalo Institutional Review Board (UBIRB)

Office of Research Compliance | Clinical and Translational Research Center Room 5018
[name]
UB Federalwide Assurance ID#: FWA00008824

PROTOCOL TITLE: Effects of adrenocorticotropic hormone (Acthar gel®) on recovery from cognitive relapses in MS.

to compare the magnitude of change between day 0 and 90 between the MS patients treated with Acthar and the previously collected controls. Analysis of variance will also be used to compare the magnitude of cognitive recovery after corticosteroid treatment to that after Acthar treatment.

The difference between the means at Day 0 and Day 90 will be used to calculate Cohen's d for each group. To facilitate analysis, all data will be normalized using a large previously published control sample.¹³ All tests will be performed based on an alpha of 0.05. Net effect sizes removing estimated practice effects will be calculated using Cohen's d.

11.2 Provide a power analysis.

The selection of 30 as the target enrollment is based on the previously completed study of 25 relapsing and 25 stable MS patients. Five additional patients are planned in order to increase the power of subsequent analyses. A power analysis based on the observed effect of corticosteroids in the relapsing group of $d = .56$ with 30 participants will be powered $>85\%$ to detect effects of a moderate magnitude from Acthar.

11.3 Describe the steps that will be taken to secure the data (e.g., training, authorization of access, password protection, encryption, physical controls, certificates of confidentiality, and separation of identifiers and data) during storage, use, and transmission.

All clinical and neurometric assessments will be conducted under the supervision of the PI. All members of research team will complete relevant training programs and courses, including but not limited to: HIPAA, CITI and GRP.

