23.0 Local Number of Subjects

23.1 Indicate the total number of subjects to be accrued locally.

University at Buffalo Institutional Review Board (UBIRB)

Office of Research Compliance | Clinical and Translational Research Center Room 5018
[name]
UB Federalwide Assurance ID#: FWA00008824

PROTOCOL TITLE: Effects of adrenocorticotrophic hormone (Acthar gel®) on recovery from cognitive relapses in MS.

We will enroll 30 relapsing-remitting MS patients and 30 stable MS patients.

23.2 If applicable, distinguish between the number of subjects who are expected to be enrolled and screened, and the number of subjects needed to complete the research procedures (i.e., numbers of subjects excluding screen failures.)

During routine clinic appointments, cognitively relapsing patients will be assessed (by the treating clinician) for suitability for the study. Subjects who agree to participate and pass screening requirements will be enrolled in the study. Thirty relapsing MS patients and 30 stable MS controls will be enrolled.

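### The stable controls are called matched, but matching is undefined, sections 11.1 and 23 disagree on who the controls are, and the ANOVA of change adjusts for nothing

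*Combined protocol and SAP*

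**What the plan says.** Section 1.1 introduces the stable group to account for practice effects over three months of repeated testing: "we will compare the results to a matched sample of MS patients who are clinically stable". Section 7.1 describes the study as open-label and mentions only comparison with a stable MS control group.

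The analysis, in section 11.1, uses ANOVA to "compare the magnitude of change between day 0 and 90 between the MS patients treated with Acthar and the previously collected controls". It then derives net effect sizes with estimated practice removed. The only adjustment of scores it names is normalisation to a published control sample.

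Section 23.1 says "We will enroll 30 relapsing-remitting MS patients and 30 stable MS patients". Section 23.2 repeats it: "Thirty relapsing MS patients and 30 stable MS controls will be enrolled".

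Section 11.2 mentions an earlier cohort, as the source of the sample size: "The selection of 30 as the target enrollment is based on the previously completed study of 25 relapsing and 25 stable MS patients".

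**The concern.** Acthar is not randomised here. The claim that the stable group's change estimates the practice gain of treated patients rests on the two groups being comparable, and the only support offered for that is the word *matched* in section 1.1. If it has no content, a difference in who the two groups are can be reported as an effect of Acthar, or can hide one.

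Practice gain can vary with age, education and general ability. When the groups differ on such a factor and the analysis does not account for it, the net effect size is wrong by that difference times the slope of practice gain on the factor. A report could then describe a matched practice correction that readers could not check.

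**Working it through.** **1. What the plan's own figure covers.** Section 11.2 claims power above 85% from d = 0.56 with 30 participants. Assume a two-sided alpha of 0.05 and d in SD units of change.
- Within-group test, n = 30: noncentrality 0.56 × √30 = 3.07. Power is 84.2% by noncentral t and 86.6% by the normal approximation. This fits the stated figure.
- Between-group test, 30 v 30: standard error √(1/30 + 1/30) = 0.258 SD. Power is 56.9% by noncentral t.

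The stated power therefore fits change within the relapsing group. It does not describe the contrast with stable controls, which is where the practice correction is made.

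**2. The sections side by side.**

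| Question | Section 1.1 | Section 11.1 | Section 23 |
|---|---|---|---|
| Who are the controls? | A matched stable sample | Controls already collected | Stable patients to be enrolled |
| How many? | Not given | Not given | 30 |
| Matched on what? | Not given | Not given | Not given |
| Term in the model? | – | None named | – |

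Section 3.1 gives no help: its first criterion requires a cognitive relapse, so stable patients have no stated eligibility rules. Section 8.1 calls adverse events and concurrent medications potential covariates, but these are not matching factors, and section 11.1 names no covariate for this contrast.

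**3. The bias.** Let practice gain have slope β on a factor x. The net effect is mean change on Acthar minus mean change in stable controls, so its bias from x is β × (mean x in Acthar patients − mean x in controls). The documents give neither quantity, so no figure can be put on it.

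**4. What adjustment does to precision.** Take five single-df covariates (age, sex, education, disease course, NAART) explaining an assumed share R² of the variance in change. No R² is given in the documents; 10–30% is an assumption.
- If the covariates are already balanced, the standard error ratio is √(1 − R²). At R² = 0.10 it is 0.949 and at R² = 0.30 it is 0.837, a fall of 5–16%.
- If the groups are unmatched and differ on the covariates only by chance, estimating the coefficients multiplies the variance by (N − 3)/(N − 8). With N = 60 this is 57/52 = 1.096.
  - R² = 0.10: √(0.90 × 1.096) = 0.993, a fall of 0.7%.
  - R² = 0.30: √(0.70 × 1.096) = 0.876, a fall of 12%.
- The equivalent gain in sample size in the unmatched case is 1/(0.90 × 1.096) = 1.01 to 1/(0.70 × 1.096) = 1.30, or 1–30%.

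A systematic difference on the covariates would reduce this gain further, but that is also the case in which the unadjusted contrast is biased.

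**5. Differences that adjustment cannot reach.** Section 3.1 admits relapsing patients after an SDMT decline from an earlier score, and section 9.2 uses the same screening test. Section 9.2 also gives the SDMT a second time in the baseline battery, and describes this for enrolled relapsing patients only. Selection on a low score tends to raise later change. An extra exposure before the day-0 score may lower it. Demographic matching or covariates remove neither.

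**The case against.** The strongest reply is that silence about factors does not show absence of matching. Section 1.1 does state matching, and group matching needs neither equal numbers nor controls chosen after the treated patients. Comparable controls can be picked from existing records. An unpaired ANOVA is also an ordinary choice for group-matched samples. All of this stands. A reader might infer that the controls cannot have been matched, or that neither possible control set is matched. The documents support only that matching is undefined and cannot be checked.

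A reader might also infer 25 controls against 30 Acthar patients by joining the already collected controls of section 11.1 to the earlier study in section 11.2. That section cites the 25 stable patients only as the basis for choosing 30, and the only control number stated for this study is 30. Even if 25 were right, the cost would be mainly precision: power of 52.8% instead of 56.9% at d = 0.56, with the standard error rising from 0.258 to 0.271 SD. Unequal numbers and the lack of a pairing term do not by themselves make the practice correction unlike.

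Finally, it may be said that normalising to a published sample handles demographics. It does not handle them for change: applying the same norm at both visits rescales the change, but does not equalise the practice gain expected at different ages or ability levels.

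**Conclusion.** The point holds as a gap in definition and analysis. Section 1.1 promises a matched comparison, no section says how it is achieved, sections 11.1 and 23 disagree on which patients are the controls, and the stated ANOVA would not correct an imbalance if there were one. Whichever control set is meant, the net Acthar effect as planned carries any imbalance in age, education or ability that bears on practice gain.

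The size of the bias is unknown and may be zero. The precision gain from adjustment is modest: about 1–12% off the standard error for unmatched groups of 30, given the assumed R² of 10–30% and five covariates. The larger range of 5–16% is available only if the covariates are already balanced. The main reason to adjust is confounding; precision is secondary. Adjustment would reduce demographic confounding but would not make the practice correction fully like for like, because of the SDMT selection and the extra SDMT administration.

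**What to change.** 1. Reconcile sections 1.1, 11.1 and 23: state whether the stable controls are an existing cohort or 30 newly enrolled patients, with their number, eligibility criteria and testing schedule, including whether they take the SDMT twice at baseline.
2. In section 11.1, replace the unadjusted Acthar-v-stable ANOVA with a linear model of day 0 to day 90 change on group plus age, sex, education, disease course and NAART. Do not add the day-0 cognitive score. The relapse lowers it in one group only, so adjusting would compare patients at a temporary low with stable patients who usually score at that level.
3. If the controls are newly enrolled, frequency-match them to the Acthar patients on age band, sex, education and disease course, and name these factors in section 1.1.
4. If the controls are historical, adjust for whichever of these factors were recorded; the documents do not say which were. Delete *matched* from section 1.1 unless the matching can be documented.
5. State as limits of the practice correction that relapsing patients are selected on a fallen SDMT and that the extra SDMT is described only for them.

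The cost is revised wording, a matching list if controls are enrolled, somewhat slower control recruitment, and five degrees of freedom. For enrolled patients, age, education and disease course come from screening, and NAART is already in the battery.

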2.0 Background

2.1 *Describe the relevant prior experience and gaps in current knowledge.*

Multiple sclerosis (MS) is an auto-immune disease causing inflammatory and neurodegenerative processes within the central nervous system (CNS). Supratentorial CNS damage has been shown to relate to cognitive impairment.^{1,2} The most common courses of MS (relapsing-remitting [RR] & secondary-progressive [SP]) typically present as a series of acute exacerbations or ‘relapses’ wherein significant demyelination contributes to lesion activity and clinical changes, including cognitive deterioration.³ While the rate of relapse is likely to decline over time in patients with secondary-progressive MS, relapses/exacerbations are not uncommon in this population.

Cognitive impairment constitutes a relevant clinical aspect of multiple sclerosis (MS). Depending on the disease phase and type, 40-65% of MS patients develop various degrees of cognitive dysfunction. These changes may begin very early in the disease process.^{4,5} Difficulties with learning and memory and slowed information processing speed, along with difficulties in higher order functions such as abstraction, problem solving, and behavioral inhibition impact continued employment, daily function, and overall quality of life.⁶⁻¹⁰

University at Buffalo Institutional Review Board (UBIRB)

Office of Research Compliance | Clinical and Translational Research Center Room 5018
[name]
UB Federalwide Assurance ID#: FWA00008824

PROTOCOL TITLE: Effects of adrenocorticotrophic hormone (Acthar gel®) on recovery from cognitive relapses in MS.

Quantitative measurement of cognitive impairment in MS is frequently through neuropsychological evaluation (NP). These evaluations are conducted by highly trained specialists, using a variety of psychometrically robust measures.^{12, 13} These neuroperformance measures are validated through extensive study of their relationships to clinically relevant phenomena such as employment status, functional independence, and progression as detected by MRI. Some examples of highly valid measures in MS are the Symbol Digit Modalities Test (SDMT),¹⁴ Brief Visualspatial Memory Test- Revised (BVMT-R),¹⁵ and Paced Auditory Serial Addition Test (PASAT).¹⁶ Relevance of these measures has been demonstrated by their relationship to cortical atrophy,^{2, 17} employment,¹³ and more common methods of clinical assessment such as walking speed and manual dexterity.¹⁸

While cognitive impairment over the span of the illness continues to be a focus of extensive research, few attempts have been made to study acute relapses with primarily cognitive sequelae (i.e., cognitive relapses).^{3, 11} This is due to the considerable methodological difficulties involved in studying the phenomenon.

2.2 Describe any relevant preliminary data.

A current study from our group, nearing completion, has demonstrated a substantial change in neuropsychological (NP) measures in MS patients with cognitive relapses ([name], et al. In Press) following treatment with high dose IV corticosteroids. Corticosteroids have been shown to promote stabilization or improvement in randomized clinical trials following acute exacerbations¹⁹ by reducing inflammation and possibly promoting re-myelination, though evidence for this is still being sought.^{20, 21} Though infusion administered corticosteroids are now accepted as the standard of care in the treatment of MS exacerbations, they are not without side effects and many patients find the infusion route of administration intolerable. Alternate treatments, particularly those demonstrated to enhance recovery in functional domains, are vitally important.

ACTH has been used for decades to treat MS exacerbations. Recent data provides evidence that the beneficial effect of ACTH in other diseases (i.e. nephrotic syndrome, opsoclonus-myoclonus and infantile spasms) may be related not only to its direct induction of corticosteroid production, but also to a corticosteroid-independent melanocortin path.²² Melanocortins have anti-inflammatory and possible neuroprotective effects and have been shown to improve attention, memory and learning. ACTH binding to central and peripheral melanocortin receptors downregulates immunocyte activity, an effect superimposed onto its

University at Buffalo Institutional Review Board (UBIRB)

Office of Research Compliance | Clinical and Translational Research Center Room 5018
[name]
UB Federalwide Assurance ID#: FWA00008824

PROTOCOL TITLE: Effects of adrenocorticotrophic hormone (Acthar gel®) on recovery from cognitive relapses in MS.

better known glucocorticoid-mediated actions. In addition, ACTH potentiates parasympathetic and SNS activity. Both lessen immune responsiveness,²² and possibly provide neuroprotective effects.

In addition to its effectiveness in treating cognitive relapses and the neuroprotective factors tentatively associated with its administration, ACTH may not only enhance initial recovery, but it may also slow the long-term progression of cognitive impairment. Therefore, we propose to study the influence of Acthar on recovery from cognitive relapses in MS, and compare this to the influence of corticosteroid administration, as well as to stable MS patients.

2.3 Provide the scientific or scholarly background for, rationale for, and significance of the research based on the existing literature and how will it add to existing knowledge.

Response: The relative frequency of cognitive relapses is unknown at this time, though the current study and past studies along the same lines are the first to work towards this identification. The measures mentioned above will be those used in identification of cognitive relapses when this topic is explored. There is limited evidence that certain neuropsychological deficits detected during an acute relapse may be reversible, particularly in patients who initially have mild cognitive impairment, with improvement being in part correlated with the reduction in acute lesion load.³

Both corticosteroids and adrenocorticotrophic hormone (Acthar) have been shown to promote stabilization or improvement in randomized clinical trials following acute exacerbations¹⁹ by reducing inflammation and possibly promoting remyelination, though evidence for this is still being sought.^{20, 21} IV Corticosteroids are typically the first choice for treatment, except in the case of patients intolerant to steroids or the infusion procedure, mostly driven by their lower cost.

ACTH has been used for decades to treat MS exacerbations. Recent data provides evidence that the beneficial effect of ACTH in other diseases (i.e. nephrotic syndrome, opsoclonus-myoclonus and infantile spasms) may be related not only to its direct induction of corticosteroid production, but also to a corticosteroid-independent melanocortin path.²² Melanocortins have anti-inflammatory and possible neuroprotective effects and have been shown to improve attention, memory and learning. ACTH binding to central and peripheral melanocortin receptors downregulates immunocyte activity, an effect superimposed onto its better known glucocorticoid-mediated actions. In addition, ACTH potentiates

University at Buffalo Institutional Review Board (UBIRB)

3.0 Inclusion and Exclusion Criteria

3.1 Describe the criteria that define who will be included or excluded in your final study sample.

Inclusion Criteria:

- (1) Identification by clinical care provider of new acute (defined by clinician as a symptom of recent origin developing with a time span of 48 hours) cognitive relapse or supratentorial GAD enhancing lesions on MRI with confirmation of cognitive decline.
 - (1a) Confirmation of cognitive decline will be obtained by administering the SDMT as a screening procedure for the study. Participants will qualify if they show a > -3 raw score point change on SDMT (relative to baseline identified to meet criteria #4).
- (2) Males/Females between the ages of 18-65 years who are capable of understanding and complying with the protocol, speak and write fluent English, and have at least a 9th grade education.
- (3) Have a diagnosis of Relapsing Remitting or early Secondary Progressive MS as per revised McDonald's Criteria.
- (4) Valid NP testing in the past 4-5 years
- (5) EDSS of ≤ 7.0
- (6) Have given written informed consent prior to any study-related procedure not part of normal medical care, with the understanding that consent may be withdrawn by the subject at any time without prejudice to his/her future medical care.
- (7) Are capable of performing the requirements of a NP test battery including at least 20/70 near visual acuity by near vision chart, with correction.

Exclusion Criteria:

- (1) Have cognitive deficits caused by concomitant medication usage or other significant neurological/psychological disease e.g. Alzheimer's disease, Parkinson's disease, stroke, transient ischemic attack, Vascular Dementia, Huntington's disease, traumatic brain injury, or chronic CNS infection.
- (2) Have evidence of any other medical cause(s) of cognitive impairment.

University at Buffalo Institutional Review Board (UBIRB)

Office of Research Compliance | Clinical and Translational Research Center Room 5018
[name]
UB Federalwide Assurance ID#: FWA00008824

PROTOCOL TITLE: Effects of adrenocorticotropic hormone (Acthar gel®) on recovery from cognitive relapses in MS.

- (3) Have evidence of current major depression as determined by a positive BDI-FS and clinician interview.
- (4) Clear new physical signs or symptoms that are referable to the spinal cord, brainstem, or optic nerve.
- (5) Evidence on MRI of new lesions in the brainstem, spinal cord, or optic nerve.
- (6) Patients with changes to medications known to influence cognition (narcotics, stimulants, etc.) or to disease modifying therapy within one month of study initiation (or within a timeframe deemed high risk by treating physician) will be excluded.
- (7) Presence of current infections as determined by clinician interview.
- (8) Currently nursing, intentionally seeking pregnancy, or deemed at-risk for unplanned pregnancy.
- (9) Any concomitant medication, or medical condition contraindicated with Acthar.

3.2 Describe how individuals will be screened for eligibility.

All participants will undergo study eligibility screening and consenting by a Clinical Research Project Coordinator. The participants will be provided with a description of the required testing for study participation, and any risks will be described in order for the person to make an informed decision regarding voluntary study participation. This is also an opportunity for the person to ask questions regarding the study and the testing components. All study participants who choose to enroll in the study will be asked to sign and date the consent form in front of the Study Coordinator.

3.3 Indicate specifically whether you will include or exclude each of the following special populations: (You may not include members of these populations as subjects in your research unless you indicate this in your inclusion criteria.)

- Adults unable to consent
- Individuals who are not yet adults (infants, children, teenagers)
- Pregnant women
- Prisoners

University at Buffalo Institutional Review Board (UBIRB)

Office of Research Compliance | Clinical and Translational Research Center Room 5018
[name]
UB Federalwide Assurance ID#: FWA00008824

PROTOCOL TITLE: Effects of adrenocorticotropic hormone (Acthar gel®) on recovery from cognitive relapses in MS.

- Inclusion criteria state subjects must be willing and able to comply with study procedures for the duration of the study.
- Individuals under the age of 18 will not be included
- Pregnant women will not be included
- Prisoners will not be included

3.4 Indicate whether you will include non-English speaking individuals.

Provide justification if you will exclude non-English speaking individuals.

(In order to meet one of the primary ethical principles of equitable selection of subjects, non-English speaking individuals may not be routinely excluded from research. In cases where the research is of therapeutic intent or is designed to investigate areas that would necessarily require certain populations who may not speak English, the researcher is required to make efforts to recruit and include non-English speaking individuals. However, there are studies in which it would be reasonable to limit subjects to those who speak English: e.g., pilot studies, small unfunded studies with validated instruments not available in other languages, numerous questionnaires, and some non-therapeutic studies which offer no direct benefit.)

We will not be including non-English speaking individuals. All neuropsychological measures are given in English and have not yet been translated or validated in other languages.

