The Brief Visuospatial Memory Test Revised (BVMTR)^{26,27} is a measure of episodic memory. This task presents a display of six visual designs presented on an 8.5 x 11 piece of paper for three consecutive learning trials. During each trial the stimulus is presented for 10 seconds, after which the participant is asked to draw the figures as accurately as possible in their correct locations. The six designs receive a score of 0, 1, or 2 based on accuracy and location. After a 20-25 minute delay, participants are again asked to recall and draw the designs.

The North American Adult Reading Test (NAART) is a measure of verbal ability. Patients are asked to read a list of words aloud.

Secondary measures will include: self and informant ratings of cognitive problems using the Multiple Sclerosis Neuropsychological Questionnaire,²⁸ the Expanded Disability Status Scale,²⁹ the Multiple Sclerosis Impact Scale, the Beck Depression Inventory – Fast Screen, and subscales from the Sickness Impact Profile³⁰ (an assessment of health related quality of life and activities of daily living). Incidence of adverse events and concurrent medications will also be recorded as potential covariates.

8.2 Describe any primary or secondary safety endpoints.

N/A

[figure not shown]

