9.4 Describe all drugs and devices used in the research and the purpose of their use, and their regulatory approval status.

Acthar Gel will be administered in accordance with the recommendations set forth in the package insert. The dosage may be individualized according to the medical condition of each patient. Frequency and dose of the drug may be determined by considering the severity of the disease and

University at Buffalo Institutional Review Board (UBIRB)

Office of Research Compliance | Clinical and Translational Research Center Room 5018
[name]
UB Federalwide Assurance ID#: FWA00008824

PROTOCOL TITLE: Effects of adrenocorticotropic hormone (Acthar gel®) on recovery from cognitive relapses in MS.

the initial response of the patient. Acthar Gel will be provided to the patient through the study.

As cognitive relapses are typically milder (compared to physically focused relapses) subjects will be initially dosed for 5 days and pending clinical response or adverse events treatment may be continued for the full 2 weeks in the opinion of the investigator. At study enrollment participants will be instructed on self-administration procedure and supplied with a 5-day course of Acthar® Gel (5ml/80 IU). Medication will be administered through either subcutaneous or intramuscular self-injection (selected by the patient). Patients will be instructed by trained clinical staff on self-administration and will self-administer the first injection under observation in the clinic.

9.5 Describe the source records that will be used to collect data about subjects. (Attach all surveys, scripts, and data collection forms.)

Source records include:

- Expanded Disability Status Scale (EDSS)
- Symbol Digit Modalities Test (SDMT)
- Paced Auditory Serial Addition Test (PASAT)
- California Verbal Learning Test Second Edition (CVLT2)
- Brief Visuospatial Memory Test- Revised (BVMT-R)
- MS Functional Composite (MSFC)
- Beck Depression Inventory Fast Screen (BDIFS)
- Fatigue Severity Scale (FSS)
- Multiple Sclerosis Impact Scale (MSIS)
- MS Neuropsychological Screening Questionnaire (MSNQ)
- North American Adult Reading Test (NAART)

9.6 What data will be collected including long-term follow-up.

The above-mentioned data will be collected at months 0 and 3.

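### No maximum interval from relapse onset to day 0 is stated and onset date is not a named study variable, so the unadjusted Acthar-versus-corticosteroid comparison cannot separate drug effect from timing of entry

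*Combined protocol and SAP*

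**What the plan says.** Section 3.1, criterion (1), requires the clinical care provider to identify a new, acute event, which the clinician defines as "a symptom of recent origin developing with a time span of 48 hours". The full criterion offers two routes: "cognitive relapse or supratentorial GAD enhancing lesions on MRI with confirmation of cognitive decline". Criterion (1a) confirms the decline by an SDMT screen against an earlier score, and criterion (4) asks only for "Valid NP testing in the past 4-5 years". The one-month rule in exclusion (6) concerns changes to cognition-altering medication or to "disease modifying therapy within one month of study initiation", not the relapse.

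Section 9.5 lists tests, scales and questionnaires as source records, and section 9.6 adds: "The above-mentioned data will be collected at months 0 and 3". Section 8.1 names the possible covariates: "Incidence of adverse events and concurrent medications will also be recorded as potential covariates".

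Section 11.1 measures change from day 0 to day 90 and states: "Analysis of variance will also be used to compare the magnitude of cognitive recovery after corticosteroid treatment to that after Acthar treatment". No covariate is named there. Sections 2.2 and 2.3 make the comparison with corticosteroids a stated purpose. Section 7.1 describes an open-label study, and section 23.1 enrols no corticosteroid group. The corticosteroid patients therefore appear to be those of the group's earlier study (sections 2.2 and 11.2: 25 relapsing and 25 stable patients), whose timing of entry is not described.

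**The concern.** Recovery is counted from entry, not from onset. A patient who enters later in the natural recovery has less loss left to regain by day 90, whatever the treatment. With randomised concurrent arms, delays would balance on average. Here one cohort is compared with a separately enrolled one, so nothing in the design balances them. The stable controls serve to estimate practice effects (section 1.1) and cannot remove spontaneous recovery, because they have no relapse to recover from.

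At stake is the reading of one planned test at alpha 0.05. Two equally effective treatments could show unequal recovery because of when patients entered, and the plan as written provides no variable with which to detect or correct this.

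**Working it through.** **The plan's own figure.** The documents give no figure on timing. The one usable effect size is d = .56 for corticosteroids (section 11.2). The stated power of more than 85% with 30 participants reproduces as a within-group test of change: Φ(.56 × √30 − 1.96) = Φ(1.107) = 86.6% (84.2% by the noncentral t). So .56 is taken below as the size of a within-group day 0 to day 90 change. The power figure itself has no bearing on timing.

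**What the text fixes and what it leaves open.**

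- Symptom route: speed of development is 48 hours; recency is required, but in words only.
- MRI route: new enhancing lesions with confirmed decline; no symptom date is required.
- SDMT screen: the reference score may be 4 to 5 years old, so a drop from it cannot date the relapse.
- Records and covariates (sections 8.1, 9.5, 9.6): onset date and relapse duration are not named.
- Analysis (section 11.1): no covariate is named for the corticosteroid comparison.

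**Size under stated assumptions.** Assume the loss decays exponentially with half-life h, and that entry is t days after onset. The share of the original loss recovered between day 0 and day 90 is

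R(t) = 2^(−t/h) × (1 − 2^(−90/h)).

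The second factor does not depend on t. For two equally effective treatments entered at 7 days and at t days, the ratio of recoveries is therefore 2^(−(t−7)/h). If the cohort entering at 7 days shows d = .56, the other shows .56 times that ratio.

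| h (days) | R(7) | R(14) | R(30) | d at 14 days | gap | d at 30 days | gap |
|---|---|---|---|---|---|---|---|
| 15 | 71% | 52% | 25% | .41 | .15 | .19 | .37 |
| 30 | 74% | 63% | 44% | .48 | .08 | .33 | .23 |
| 60 | 60% | 55% | 46% | .52 | .04 | .43 | .13 |

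Example, h = 30, t = 14: ratio = 2^(−7/30) = .851; .56 × .851 = .48; gap = .56 − .48 = .08.

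**Effect on the test.** Assume 30 Acthar and 25 corticosteroid patients, no true drug difference, a two-sided alpha of 0.05, and a gap expressed in SDs of change. The noncentrality is gap ÷ √(1/30 + 1/25) = 3.69 × gap. The noncentral t then gives a false-positive rate of 6.5% for a gap of .1, 11.2% for .2, 19.3% for .3 and 30.5% for .4, against the nominal 5%.

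**Through what does timing act?** In this model, change from day 0 to day 90 equals the day 0 deficit times (1 − 2^(−90/h)). Delay matters only through the deficit still present at day 0. That deficit, relative to the pre-relapse score, is already collected for the Acthar patients and belongs in the adjustment. It is measured with error against an old reference score, so the interval still adds information.

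**The case against.** Four points on the other side have weight.

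- **There is a limit, though a qualitative one.** The relapse must be new, acute and recent in the clinician's judgement; section 20.2 describes urgent visits for relapse as the source of patients; sections 1.1 and 9.2 require the enhancing lesions to be new. A reader might infer that timing of entry is wholly unrestricted. The documents do not support that; what is missing is a stated maximum. This also makes a 30-day delay an extreme case.
- **The date may be recorded.** A reader might infer that onset goes unrecorded. The list in section 9.5 is not exhaustive, since medications and adverse events are collected without being on it. Judging a 48-hour development requires an onset history, a clinical assessment precedes enrolment (section 9.2), and the data collection forms are not visible. What stands is that the protocol neither names the date as a study variable nor uses it.
- **The cohorts may not differ.** A reader might infer that the comparison is biased. No document gives the delay in either cohort, so neither the existence, the direction nor the size of a bias can be derived.
- **The model may overstate the effect.** It scales all of .56 by timing. If part of .56 is a practice effect, that part would not shrink with delay. The SDMT screen may offset some of the gap, since patients who have largely recovered should be screened out.

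These points lower the likely size. They do not answer the gap itself: an unadjusted, non-randomised comparison in which a plausible confounder is neither named nor reported.

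**Conclusion.** The point holds as an omission in the corticosteroid comparison. No maximum interval from onset to day 0 is stated, the MRI route carries no symptom date, and section 11.1 compares recovery without adjustment, so a difference in timing of entry, if there is one, would be credited to the drug.

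Under the assumed exponential recovery with half-lives of 15 to 60 days, a one-week difference in entry (14 versus 7 days) would give a spurious gap of about .04 to .15 in d, and the extreme case (30 versus 7 days) about .13 to .37. These are illustrations that also assume the earlier study's 25 relapsing patients are the comparator.

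A reader might extend the point to the whole study. That goes too far: the primary hypothesis, that Acthar patients return to baseline (section 1.2), does not rest on the corticosteroid cohort, and the stable-control comparison addresses a different question. This is a cheap improvement to one planned analysis.

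**What to change.** - **Section 9 (screening).** Name the date of symptom onset as a study variable; for MRI-route patients, also record the scan date. No change to eligibility is needed.
- **Earlier study.** Extract the same interval from its records where available.
- **Section 11.1.** Identify the corticosteroid cohort explicitly. Report the onset-to-day-0 interval by cohort. Add an adjusted Acthar-versus-corticosteroid analysis with two covariates: the day 0 deficit relative to the pre-relapse baseline, and the interval. If the earlier study lacks the interval, state that this comparison cannot be separated from timing of entry.
- **Section 3.1.** Clarify that the 48 hours refers to speed of development, if that is the intent.

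The cost is one form field (two for MRI-route patients), a chart check in the earlier cohort, and one or two degrees of freedom. The conclusion about corticosteroids may have to be worded more cautiously.
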